9.3 VARIABLES

9.3.1 Exposures

For all above samples, baseline characteristics will be described. These refer either to index date (= date of incident (first) diagnosis of COPD) or to the 12-month pre-index period:

- Age
- Gender
- Concomitant diseases /comorbidity level
 - 10 most frequently documented diseases, based on recorded ICD-10 codes up to 3rd level
 - Charlson Comorbidity Index (CCI, see Suppl. Table 3)
 - Percentage of patients with at least one confirmed inpatient or two confirmed outpatient diagnoses in two different quarters of the following diseases:
 - Asthma (J45.)
 - Bronchiectasis (J47.)
 - Bronchial carcinoma (C34.)

- Diabetes mellitus (E10.-E14.)
- Congestive heart failure (I11., I50.)
- Kidney disease (N17.-N19.)
- Myocardial infarction (I21., I22.)
- Hypertension (I10.-I15.)
- Peripheral vascular disease (I73., I74., I77.)
- Cerebrovascular event or transient ischemic attack (I60.-I69., G45.)
- Hemiplegia (G81.)
- Dementia (F00.-F03.)
- Sleep apnoea (G47.3)
- Osteoporosis (M80., M81.)
- Percentage of patients with at least one confirmed inpatient or two confirmed outpatient diagnoses in two different quarters of the following respiratory diseases: ICD-10 codes J0-J99 (Top-5 diseases as observable for sample COPD-12 and COPD-FULL SAMPLE will be reported)
- Previous drug treatment in the pre-index period, based on appropriate ATC group level
 - Percentage of patients who received specific treatments (most common 10 treatments as observable for above samples) with at least two prescriptions in the pre-index period

9.3.2 Outcomes

9.3.2.1 Primary outcomes

The primary objective of this study is to describe the real-life drug treatment of patients with incident COPD, including description of treatment sequence/escalation in the first 12/24/36 months after incident diagnosis. This analysis will be based on the following samples:

- COPD-12: All incident COPD patients with a follow-up of 12 months since index date (analysis will be done for the first 12 months of observation)
- COPD-24: All incident COPD patients with a follow-up of 24 months since index date (analysis will be done for the first 24 months of observation)
- COPD-36: All incident COPD patients with a follow-up of 36 months since index date (analysis will be done for the first 36 months of observation)
- COPD FULL DATA: All incident COPD patients. (analysis will be done for the full observation period)
- COPD DMP-12: All incident COPD patients with available DMP data (at least one entry after index date) and a follow-up of 12 months since index date (analysis will be done for the first 12 months of observation)

In this analysis, baseline treatment as well as treatment cascades including mean duration of treatment in the pre-defined follow-up periods will be assessed. Results will be reported as follows:

- Mean number of different agents an observed patient received (per patient year)¹³
- List of most frequently prescribed agents (based on [Suppl. Table 2](#)) including percentage of patients who received these agents
- Longitudinal analysis of treatment patterns/cascades with long-acting bronchodilators and ICS, as described in [Table 2](#). Here, proportion of observed patients whose treatment can be described by the pre-defined treatment patterns will be assessed.

Table 2

Description of treatment patterns/cascades (template for reported outcomes)^{14,15}
(please note: below table might not show all theoretically possible treatment patterns. In the analysis, based on observed treatment patterns, all treatment pattern combinations that were observed in >5% of the patient population will be reported)

Therapy pattern after index date	1st line	2nd line	3rd line	4th line	N (%) of patients
Mono, no switch during follow-up period	LAMA	-	-	-	...
	LABA	-	-	-	...
	ICS	-	-	-	...
Mono, with switch	LAMA	LABA	-	-	...
	LAMA	ICS	-	-	...
	LABA	LAMA			
	LABA	ICS			
	ICS	LABA			
	ICS	LAMA			

¹³ Even if this study is based on fixed follow-up periods, death of some patients during the follow-up period might lead to shorter follow-up periods than 12, 24, or 36 months in some patients. That is why above numbers will be reported per observed patient year.

¹⁴ Analyses will be done for all three defined follow-up periods (12 months, 24 months, 36 months). For major treatment patterns, characteristics of respective patients will be described.

¹⁵ Switching between different drugs of the same drug class (LAMA,LABA,ICS) will not be taken into account for this analysis.

Table 2 (cont'd)

Description of treatment patterns/cascades (template for reported outcomes)
 (please note: below table might not show all theoretically possible treatment patterns. In the analysis, based on observed treatment patterns, all treatment pattern combinations that were observed in >5% of the patient population will be reported)

Therapy pattern after index date	1st line	2nd line	3rd line	4th line	N (%) of patients
Mono, with switch to dual therapy	LAMA	LAMA+LABA	-	-	...
		LAMA+ICS			
		LABA+ICS			
	LABA	LAMA+LABA		-	
		LAMA+ICS			
		LABA+ ICS			
Mono, with switch to dual therapy and subsequent switch to another dual therapy	LAMA	LAMA+LABA	LAMA+ICS		
		LAMA+ICS	LAMA+LABA		
		LABA+ICS	LABA+ICS		
	LABA	LABA+LAMA	LABA+ICS		
		LABA+ ICS	LABA+LAMA		
		LAMA+ICS	LAMA+ICS		
Mono, with switch to dual therapy and subsequent triple therapy	LAMA	LAMA+LABA	LAMA+LABA+ICS	-	...
		LAMA+ICS	LAMA+LABA+ICS		
	LABA	LAMA+LABA	LAMA+LABA+ICS	-	
		LABA+ ICS	LAMA+LABA+ICS		
Mono, with switch to triple therapy	LAMA	LAMA+LABA+ICS			
	LABA	LAMA+LABA+ICS			

Table 2 (cont'd)

Description of treatment patterns/cascades (template for reported outcomes)
 (please note: below table might not show all theoretically possible treatment patterns. In the analysis, based on observed treatment patterns, all treatment pattern combinations that were observed in >5% of the patient population will be reported)

Therapy pattern after index date	1st line	2nd line	3rd line	4th line	N (%) of patients
Dual therapy, no switch during follow-up period	LAMA+LABA LABA+ICS LAMA+ICS	- - -	- - -	- - -	...
Dual therapy with switch to another dual therapy	LAMA+LABA LAMA+ICS LABA+ICS	LAMA+ICS LAMA+LABA LAMA+ICS	LAMA+LABA LAMA+ICS		
Dual therapy with switch to triple therapy	LAMA+LABA LAMA+ICS LABA+ICS	LAMA+LABA+ ICS LAMA+LABA+ ICS LAMA+LABA+ ICS	-		
Triple therapy, no switch during follow-up period	LAMA+LABA+ICS				

Table 2 (cont'd)

Description of treatment patterns/cascades (template for reported outcomes)
(please note: below table might not show all theoretically possible treatment patterns. In the analysis, based on observed treatment patterns, all treatment pattern combinations that were observed in >5% of the patient population will be reported)

Therapy pattern after index date	1st line	2nd line	3rd line	4th line	N (%) of patients
Triple therapy, de-escalation during follow-up	LAMA+LABA+ICS	LAMA+LABA LAMA+ICS LABA+ICS			...
Dual therapy, any downgrading during follow-up	LABA+ICS LABA+ICS LAMA+ICS LAMA+ICS LABA+LAMA LABA+LAMA	LABA ICS LAMA ICS LABA LAMA			

Others

For the most common Top-5 treatment cascades, duration of treatment of each line of therapy as well as characteristics of patients that could be assigned to the specific cascades will be reported.

Please note that a specific combination therapy will be assumed to have been prescribed if there was a prescription of a respective combination agent. In case separate agents were prescribed, two scenarios are applied: (1) A combination treatment is assumed to have been prescribed if the respective agents were prescribed at the same day or (2) a combination treatment is assumed to have been prescribed if the respective agents were prescribed within a 21 days window and a similar prescription behavior was repeated at least one additional time (example – assumed LABA+LAMA combination: LABA prescription day 1,

LAMA day 10, LABA day 91, LAMA day 96). Coverage calculation (days covered by a respective treatment pattern) will be based on the defined daily dosage (DDD) of each prescription.

An agent will be considered as discontinued if a supply gap of at least 60 days (sensitivity analysis: 15/30/90 days) is observed.

In an additional Kaplan Meier analysis, time to start of a dual therapy (LAMA+LABA/LABA+ICS/LAMA+ICS) and time to start of a triple therapy (LAMA+LABA+ICS) will be assessed (days from incident diagnosis until first day of triple

therapy). This analysis will be based on the COPD full data sample, i.e. no fixed follow-up period but patient-specific follow-up periods (until end of observational period or until censoring or until date of event, whatever comes first) will be applied.

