9.2 SETTING

An anonymized dataset from the cooperating sickness funds, which includes all patients with at least one COPD diagnosis, who were insured by this sickness funds for the entire period (01/01/2013 - 30/06/2018) will be available.

A patient will be confirmed as being COPD-incident if specialists documented at least two confirmed outpatient COPD diagnoses (ICD J44.-) and/or at least one inpatient COPD diagnosis (ICD J44.-), without such diagnoses in the previous 12 months and without any COPD prescription in the previous 12 months (Suppl. Table 2).

Specific inclusion criteria can be described as follows:

- All patients should have been covered by the sickness fund for the entire period (01/01/2013-30/06/2018) or, in case a patient deceased after index date, for the time until death
- A patient will be included as an incident COPD patient if either a hospital documented at least one COPD diagnosis (ICD-10 J44.-) or a specialist (pneumologist) documented at least two confirmed COPD diagnoses (above ICD-10 code) in two different quarters; the first of the above diagnoses is defined as index diagnosis; inclusion period is defined as lasting from 01/01/2014 until 30/06/2017

- Patients should not have received any COPD diagnosis (ICD-10 J44.-) or any COPD-associated medication (Suppl. Table 2)⁹ in the 12 months pre-index period
- Patient should have, at date of incident COPD diagnosis (index date), an age of at least 40 years

Patients who received at least one confirmed inpatient asthma diagnosis or two confirmed outpatient diagnoses of asthma (ICD-10: J45.-) by pneumologists after the incident COPD diagnosis (index diagnosis) will be separately observed.

Based on these inclusion/exclusion criteria, the following data sets will be analyzed (Figure 3)¹⁰:

- COPD-FULL DATA: All incident COPD patients with a follow-up of up to 54 months
- COPD-12: All incident COPD patients with a follow-up¹¹ of 12 months since index date
- COPD-24: All incident COPD patients with a follow-up of 24 months since index date
- COPD-36: All incident COPD patients with a follow-up of 36 months since index date
- COPD DMP-FULL DATA: All incident COPD patients with available DMP data (at least one entry during 3 months after index date¹²) and a follow-up of up to 54 months.
- COPD DMP-12: All incident COPD patients with available DMP data (at least one entry during 3 months after index date) and a follow-up of 12 months since index date

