- COPD DMP-24: All incident COPD patients with available DMP data (at least one entry during 3 months after index date) and a follow-up of 24 months since index date
- COPD DMP-36: All incident COPD patients with available DMP data (at least one entry during 3 months after index date) and a follow-up of 36 months since index date.

⁹ Prescription of systemic/oral corticosteroids (SCS/OCS) will not be considered as exclusion criteria

¹⁰ Please note that this samples will not include patients with at least one confirmed inpatient or two confirmed outpatient diagnoses of asthma (ICD-10: J45.-) by pneumologists after the incident COPD diagnosis (index diagnosis) during the follow-up period. Those patients will be described separately.

[figure not shown]
¹¹ Time since patient-individual index date until 30/06/2018; patients who died within this period will not be excluded from the analysis

¹² So far it is unknown how many patients were included in the DMP directly after incident diagnosis and for how many patients an entry in the first months after diagnosis will be available. Thus, depending on the pattern that will be observed in the data, the restriction „at least one entry during the 3 months after index date“ might be extended to „at least one entry during the 6/12 months after index date“.

Figure 3

Baseline period, inclusion period, follow-up period for different study samples

(note: for time to event analyses, COPD-full data sample (with full follow-up times) will be applied). DMP: disease management program (refers to the subsample of patients who participate in the COPD DMP and thus provide more detailed data)

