9.3.2.2 Secondary outcomes

First Secondary

Comparison of initial drug treatment with treatment guidelines

Comparison of real-world treatment of patients with guidelines will be done based on two samples: COPD-12 and COPD DMP-12. Assessment will generally be done for two time points:

- For all patients at index date (+ 4 weeks)
- For patients who received a triple combination (LABA+LAMA+ICS) at first day of triple therapy prescription.

Prescription patterns will be compared with German treatment guideline recommendations. Here, the 2018 S2 guideline [1] will be used (sensitivity analysis: 2012 guideline, which is an updated version of the 2006 guideline [2]). Obviously, as patients are only observed until mid of 2018, it cannot be expected that they were treated in line with the 2018 S2 guideline. However, this analysis describes potential needs to adapt the current treatment of the patients in the future, and is as such important for preparation of later initiatives to optimize the treatment of the patients.

Based on claims data only, assessment of the severity of the COPD disease for COPD patients is hardly possible. The reason is that neither FEV₁ data nor symptoms' data as measured by the COPD assessment test (CAT) or the Modified Medical Research Council (mMRC) are available in a claims dataset. So, for the comparison of the real-world treatment with 2018/2012 guideline recommendations, based on sample COPD-12, the following analyses will be done:

- COPD-12, at index date
 - Based on the inclusion criteria, an incident COPD patient did not experience any exacerbation in the previous 12 months, as no such diagnosis was documented. So, the initial treatment with long-acting bronchodilators should generally not include use of ICS (both guidelines). Moreover, based on the 2012 guideline, a therapy with long-acting bronchodilators should start with either a LAMA or a LABA, but not with a combination of them.

So, based on these criteria, the following percentages will be reported:

- Percentage of patients not treated in line with 2018 guideline
 - Therapy at index date includes ICS
- Percentage of patients not treated in line with 2012 guideline
 - Therapy at index date includes ICS or a LABA/LAMA combination or triple therapy of LABA+LAMA+ICS¹⁶
- COPD-12, at first date of an observed LABA+LAMA+ICS combination, which is not the index date

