9.3.2 Outcomes? (e.g. International Classification of Diseases (ICD)-10, Medical Dictionary for Regulatory Activities (MedDRA))				
9.3.3 Covariates?				
9.4 Is a linkage method between data sources described? (e.g. based on a unique identifier or other)				

Comments:

Section 10: Analysis plan	Yes	No	N/A	Section Number
10.1 Is the choice of statistical techniques described?				9.7
10.2 Are descriptive analyses included?				9.7
10.3 Are stratified analyses included?				
10.4 Does the plan describe methods for adjusting for confounding?				9.7
10.5 Does the plan describe methods for handling missing data?				9.7.2
10.6 Is sample size and/or statistical power estimated?				9.7

Comments:

Section 11: Data management and quality control	Yes	No	N/A	Section Number
11.1 Does the protocol provide information on data storage? (e.g. software and IT environment, database maintenance and anti-fraud protection, archiving)				9.6
11.2 Are methods of quality assurance described?				9.8
11.3 Is there a system in place for independent review of study results?				9.6

Comments:

Section 12: Limitations	Yes	No	N/ A	Section Number

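### The 12-, 24- and 36-month treatment summaries come from nested samples with different index periods, and no visible analysis shows results by index year

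*Combined protocol and SAP*

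**What the plan says.** Section 9.2 fixes the index dates: "inclusion period is defined as lasting from 01/01/2014 until 30/06/2017". Its footnote on follow-up defines the available time as "Time since patient-individual index date until 30/06/2018" and keeps patients who die, so the potential time to that date decides who belongs to a fixed-length sample.

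Section 9.3.2.1 lists the samples for the primary objective, among them "COPD-12: All incident COPD patients with a follow-up of 12 months since index date", "COPD-24: All incident COPD patients with a follow-up of 24 months since index date" and COPD-36. Each is analysed over its own window; for COPD-36, "analysis will be done for the first 36 months of observation". The results are baseline treatment, number and frequency of agents, and the Table 2 patterns, and a footnote to Table 2 asks for the patterns at all three horizons. Kaplan-Meier analyses of time to dual and to triple therapy use the full sample, defined in 9.2 as "COPD-FULL DATA: All incident COPD patients with a follow-up of up to 54 months".

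The guideline comparison (9.3.2.2, First Secondary) is reported in COPD-12 and COPD DMP-12 as pooled percentages. Its stated use is that "this analysis describes potential needs to adapt the current treatment of the patients in the future".

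Index year is not among the baseline characteristics in 9.3.1 and appears in no visible analysis in 9.3.2 or 9.7.1. In the Annex 2 checklist, item "10.3 Are stratified analyses included" is ticked No. Sections 9.9 and 9.12 do not mention calendar time.

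**The concern.** The primary objective concerns sequence and escalation over the first 12, 24 and 36 months, so the three sets of results will be set side by side. A reader who sees a class used more, or less, at 36 months than at 12 will tend to take that as the course of treatment. Part of it may only reflect that the 36-month figures describe people diagnosed earlier.

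This is clearest for baseline treatment. It is measured at the same point of disease in every sample, so a difference between samples cannot be escalation. The Table 2 percentages inherit the same shift through their first-line column.

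Calendar change in these categories is plausible on the protocol's own account. Section 7 refers to increasing evidence on ICS and cites trials published in 2014 and 2016, the second after the COPD-36 index dates close. Section 9.3.2.2 says that starting on LABA plus LAMA counts as a deviation under the 2012 guideline but not under the 2018 one. For the guideline percentages, one figure pooled over 2014 to mid-2017 cannot show whether the latest starters, who are closest to the stated use, differ from the earliest.

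**Working it through.** **Inputs.** Index dates 01/01/2014 to 30/06/2017 and data end 30/06/2018 (9.2); windows of 12, 24 and 36 months (9.3.2.1); N>40,000 incident patients, about 26,000 (~65%) with a long-acting bronchodilator (9.5). Assumed: even accrual over the index period, and the same 65% in every sample.

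**The plan's own figures.** 01/01/2014 to 30/06/2018 is 4 × 12 + 6 = 54 months, as stated in 9.2. 0.65 × 40,000 = 26,000, as stated in 9.5.

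**Index windows.** Latest index date = 30/06/2018 minus the follow-up required. Mean index date = 01/01/2014 plus half the window.

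| Sample | Index dates end | Window | Share of COPD-12 | Approx. N | Mean index date |
|---|---|---|---|---|---|
| COPD-12 | 30/06/2017 | 42 months | 100% | 40,000 | 01/10/2015 |
| COPD-24 | 30/06/2016 | 30 months | 30/42 = 71% | 28,600 | early 04/2015 |
| COPD-36 | 30/06/2015 | 18 months | 18/42 = 43% | 17,100 | 01/10/2014 |

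Mean index date gap, COPD-12 versus COPD-36: 42/2 − 18/2 = 12 months. Share of COPD-12 that cannot enter COPD-36: 24/42 = 57%. Index dates in 2016-17 make up 18/42 = 43% of COPD-12, 6/30 = 20% of COPD-24 and none of COPD-36.

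**Possible artefact.** The documents give no trend, so the drift is an assumption. If the share of an initial regimen moves linearly by b points a year with calendar time and nothing else changes, the difference between samples is b × gap in years:

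- COPD-12 versus COPD-36 (1 year): 1, 2 or 5 points for b = 1, 2 or 5.
- COPD-12 versus COPD-24 (0.5 year): 0.5, 1 or 2.5 points.

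**Sampling error for scale.** 95% half-width = 1.96 × √(p(1−p)/n).

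- All of COPD-36, p = 20%, n = 17,143: 1.96 × √(0.16/17,143) = 0.6 points.
- Bronchodilator users, p = 30%: 0.6 points in COPD-12 (n = 26,000) and 0.9 in COPD-36 (n about 11,100).

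**More data.** The protocol allows further 2018 quarters. With data to 31/12/2018 and the inclusion period unchanged, COPD-36 would take 24 months of index dates, and the gap would be 42/2 − 24/2 = 9 months. It narrows but does not close.

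**The case against.** The strongest reply is that the escalation result does not depend on comparing samples. Table 2 follows the same patients from first to fourth line within each sample, and the Kaplan-Meier analyses follow one sample from diagnosis. Cost by year since diagnosis is also compared inside COPD-36. This stands. A reader might infer that the escalation analysis is itself assembled from different patients at different horizons, or that only cost is followed within one sample. The documents support neither. The curve helps only in part, since beyond 36 months it rests on people diagnosed before mid-2015.

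The samples are also nested rather than separate, and no test between horizons is planned. Both are true. They limit the point to how the three descriptive summaries are read together.

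The size is assumed. Section 7 cites the trials to say that early ICS use may persist despite the evidence, which does not document a change in prescribing. A reader should not infer that a drift has been shown.

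Redactions matter as well. Section 9.3.3 has no visible content, sections after 9.3.2.2 and 9.7.1 are removed, and part of Table 4 is unreadable. The regression covariates are not listed in the visible text, so index year cannot be called excluded. The checklist's No on stratification is general and stands beside a Yes on effect modifiers.

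Finally, the guideline comparison does not suffer from a change of sample between horizons, and the protocol concedes that patients could not be expected to follow the 2018 guideline. The remaining issue there is narrower: the pooling over index years.

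**Conclusion.** The point holds for comparisons between the three horizons and for the pooled guideline percentages. The different index windows follow directly from the protocol's dates. The 12-month gap and the 57% rest on even accrual. An artefact of 1 to 5 points rests on an assumed linear drift of 1 to 5 points a year; any such drift would be at or above the sampling half-width of about 0.6 to 0.9 points, so the confidence intervals would not warn the reader. The statement that nothing is shown by index year covers the visible text and the checklist only.

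This is a worthwhile reporting change in a mainly descriptive study. It does not invalidate the within-sample sequences or the time-to-event results.

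**What to change.** 1. In 9.3.2.1, keep the three samples and also report the 12- and 24-month results inside COPD-36, and the 12-month results inside COPD-24. Within COPD-36 all horizons then share index dates 01/01/2014 to 30/06/2015, and the gap in mean index date falls from 12 months to 0.
2. Report initial treatment, ICS-containing initial treatment and the 2012 and 2018 guideline percentages by index year: 2014, 2015, 2016 and first half of 2017.
3. Name index year as a covariate in the logistic regression for guideline-concordant treatment (Table 4).
4. State in 9.7.1 or 9.9 that differences between samples are not to be read as escalation. State too that, even inside COPD-36, calendar time and time since diagnosis advance together, so step 1 removes the change in patients but not every calendar effect.

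The cost is more table columns and smaller counts per index year, with the half-year of 2017 the smallest (6/42, about 14% of COPD-12). No new data are needed, and no patients are lost from the planned analyses.

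### COPD DMP-12 has two conflicting entry rules (within 3 months in 9.2, any time after index in 9.3.2.1), and the looser the rule, the more membership depends on surviving to a DMP entry

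*Combined protocol and SAP*

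**What the plan says.** Section 9.2 (Setting) lists the analysis samples and gives this rule: "COPD DMP-12: All incident COPD patients with available DMP data (at least one entry during 3 months after index date". DMP-24, DMP-36 and DMP-FULL DATA carry the same 3-month condition.

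Section 9.3.2.1 (Primary outcomes) lists COPD DMP-12 again among the samples for the treatment description. There the condition reads "at least one entry after index date) and a follow-up of 12 months since index date". It states no time limit and does not refer back to 9.2.

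Footnote 12 in 9.2 explains that it is not yet known how many patients have an early DMP entry. It then says that, "depending on the pattern that will be observed in the data", the 3-month condition may be relaxed to "at least one entry during the 6/12 months after index date". No threshold is given.

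On deaths, footnote 11 in 9.2 says "patients who died within this period will not be excluded from the analysis". Footnote 13 in 9.3.2.1 reports results per observed patient year because "death of some patients during the follow-up period might lead to shorter follow-up periods than 12, 24, or 36 months in some patients". Observation starts at the index date in every sample.

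**The concern.** A programmer working from 9.2 and one working from 9.3.2.1 would build different samples under one name. The difference is systematic. The DMP entry that decides membership happens after index, while follow-up is counted from index. Anyone who dies between index and a would-be entry drops out of the sample, whatever footnote 11 intends about keeping deaths. Members' time from index to entry is therefore free of death by construction.

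This condition already exists under the 3-month rule, where it is small. It becomes large if the open-ended wording is followed, or if the window is widened under footnote 12. The available text provides for no landmark, delayed entry or time-varying DMP status, and section 9.12 (Bias) does not mention the issue. At stake is whether the DMP results describe incident DMP patients or only those who lived long enough to be documented.

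**Working it through.** The plan states no figure to reproduce here, so the check compares the definitions and then illustrates the survival condition.

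**Step 1: how late can a qualifying entry fall?** Index dates run from 01/01/2014 to 30/06/2017 and data end on 30/06/2018 (9.1, 9.2).
- Index 01/01/2014: 1,641 days / 30.4375 = 53.9 months, which agrees with the DATA samples' "All incident COPD patients with a follow-up of up to 54 months".
- Index 30/06/2017: 365 / 30.4375 = 12.0 months.

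Under 9.3.2.1 the entry can thus come 12 to 54 months after index, depending on the patient. Under 9.2 the limit is 3 months.

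**Step 2: effect of the window on the sample.** Assumptions, none of them from the documents: 12-month mortality M of 5%, 10% or 15%; constant monthly hazard h = −ln(1 − M)/12; would-be first entry time u uniform on 0 to W months; membership only if alive at u.

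- Share of would-be entrants alive at entry: A = (1 − e^(−hW)) / (hW).
- Apparent 12-month mortality among members, for W ≤ 12: 1 − (1 − M)/A.
- For W > 12, members whose entry falls after month 12 cannot die in the first 12 months. The expression becomes (1/W) × [M/h − 12(1 − M)] / A.

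With M = 10%, h = 0.00878 per month:
- W = 3: A = 0.9869; 1 − 0.90/0.9869 = 8.8%.
- W = 12: A = 0.9491; 1 − 0.90/0.9491 = 5.2%.
- W = 54: A = 0.7964; (1/54) × (11.39 − 10.80) / 0.7964 = 1.4%.

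All scenarios:

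| Window W (months) | Apparent, M = 5% | Apparent, M = 10% | Apparent, M = 15% | Death-free share of members' first-12-month person-time (M = 10%) |
|---|---|---|---|---|
| 3 | 4.4% | 8.8% | 13.3% | 13% |
| 6 | 3.8% | 7.6% | 11.5% | 26% |
| 12 | 2.5% | 5.2% | 7.9% | 50% |
| 24 | 1.3% | 2.7% | 4.3% | 74% |
| 54 | 0.6% | 1.4% | 2.3% | 87% |

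The last column is members' time from index to entry, capped at 12 months, divided by their total person-time in the first 12 months, by numerical integration. The 54-month row is the extreme case, since only patients indexed at the start of 2014 have that much time.

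**Step 3: which analyses use a DMP sample?**
- Treatment description (9.3.2.1): five samples, of which only DMP-12 needs a DMP entry.
- Exacerbation frequency (9.3.2.2, Second Secondary): DMP-12, -24 and -36 are included and rates are per patient-year, so they are affected. The time before entry is protected from death but not from exacerbations. Any distortion comes through the loss of patients who die early, and the documents do not allow its size to be estimated.
- Cost and resource use (9.3.2.2, Third Secondary): participants are compared with non-participants. No entry window is stated, so the same problem may arise.
- Guideline comparison (9.3.2.2, First Secondary): at index there is no additional DMP analysis. At first triple therapy, only patients with a DMP entry before that prescription are included.

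**The case against.** The strongest reply is that 9.3.2.1 is shorthand. Section 9.7.1 says the samples were defined earlier, and 9.2 spells out the 3-month rule for every DMP sample. That is plausible, but 9.3.2.1 restates the condition in different words without a reference back, so the two sections still have to be reconciled. The conflict in wording reaches DMP-12 only.

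The plan can also fairly say that footnote 12 is an openly stated feasibility provision. A reader might infer that the window could be chosen to suit the results. The text does not support that: the footnote opens with uncertainty about how many patients have an early entry, so the pattern it refers to is most naturally entry timing. What stands is that it gives no criterion and does not say that the decision precedes sight of treatments and outcomes.

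A reader might further infer that the primary analysis as a whole, or the DMP guideline check, rests on a survivor-selected sample. Neither holds. Four of the five primary samples need no DMP entry, and the Kaplan-Meier analyses use COPD-FULL DATA. The guideline check at first triple therapy already requires a prior entry and looks backward from that date, so deaths before entry create no death-free follow-up in that percentage.

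Finally, moving the start of all DMP follow-up to a landmark would discard the initial treatment that the study sets out to describe. A 3-month landmark leaves 9 of DMP-12's 12 months, and a 12-month landmark leaves none. That objection stands, and a landmark belongs in a sensitivity analysis only.

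**Conclusion.** The point holds in limited form. One named sample has two membership rules, and a third or fourth is possible under footnote 12. The choice matters because survivor selection grows with the window. Under an assumed 10% 12-month mortality, apparent mortality among members falls short by 1.2 percentage points with the 3-month rule (10% − 8.8%), by 4.8 points with 12 months (10% − 5.2%), and by more with the open-ended rule. The direction is the same for assumed mortality of 5% to 15%. The size rests on assumed mortality, a constant hazard and uniform entry times, none of which the documents supply.

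The consequences are confined to the DMP-12 treatment description, the DMP exacerbation rates and possibly the DMP versus non-DMP cost comparison. COPD-12, -24, -36 and FULL DATA are unaffected.

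**What to change.** 1. In 9.3.2.1, replace the open-ended condition with the 9.2 rule (entry within 3 months of index). This also fits the Abstract's remark that the DMP data are usable only if documentation starts soon after diagnosis.
2. In footnote 12, state that any widening to 6 or 12 months will be decided from the distribution of DMP entry dates alone, before treatments or outcomes are tabulated, and will apply identically to all DMP samples.
3. Keep the index-based DMP tables, labelled as conditional on survival to DMP entry.
4. Add a sensitivity analysis of DMP exacerbation rates that counts person-time from DMP entry (delayed entry), or from a 3-month landmark among members alive then. If the window is widened, delayed entry is the workable choice.
5. State the entry window that defines a DMP participant in the cost comparison.

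The cost is a smaller DMP-12 sample than under the open-ended rule, plus a little extra analysis. The loss of patients cannot be quantified in advance. Section 9.5 expects about 30% of more than 40,000 patients (0.30 × 40,000 = 12,000) to have at least one DMP documentation, but it states no window for that figure. No new data are needed.
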